### 1.3 Rationale for Current Protocol

The purpose of this protocol is to collect long-term follow-up information on the safety and efficacy of islet transplantation in CIT subjects after their completion in their CIT parent study.

## 1.4 Known and Potential Risks and Benefits to Human Subjects

Administration of all immunosuppressive and immunomodulatory therapies used presently to prevent rejection of transplanted tissues carry general risks of opportunistic infection and malignancy, including lymphoma (~1%), and skin cancers. These agents are not recommended for nursing mothers, and it is recommended (and mandated in the current protocol) that women of childbearing potential use effective contraception before, during and for at least 4 months following administration of these agents.

The agents listed below are those currently used in the parent trials. We anticipate that these will be used in CIT08. However, it is possible that this can change due to changes in drug availability.

### 1.4.1.1 SIROLIMUS (RAPAMUNE®)

The FDA approved sirolimus (rapamycin, Rapamune®) as an immunosuppressive agent in 1999 (see product monograph for details). In 208 kidney transplant recipients receiving 5 mg of sirolimus daily compared to 124 receiving placebo, there was an increased incidence of hypercholesterolemia (46 vs. 23%), hyperlipemia (57 vs. 23%), rash (20 vs. 6%), arthralgia (31 vs. 18%), diarrhea (35 vs. 27%), anemia (33 vs. 21%), leucopenia (13 vs. 8%), thrombocytopenia (30 vs. 9%), and hypokalemia (17 vs. 9%). Side effects are related to drug concentration and are improved with maintenance of the sirolimus 24-hour trough level between 10–20 ng/mL.

Of infections, only mucosal herpes simplex virus (HSV) occurred at a greater rate with sirolimus. There was no increase in rate of malignancy (3.4 vs. 3.1%). While sirolimus was originally proposed as a non-nephrotoxic agent, it is becoming apparent that sirolimus-associated nephrotoxicity does occur in clinical practice. Crew *et al.* described two patients with thrombotic microangiopathy secondary to sirolimus exposure. Sirolimus alters the pharmacokinetic profiles of other CNIs (*e.g.*, tacrolimus) and may thereby potentiate nephrotoxicity. Fervenza *et al.* described nephrotoxicity from sirolimus in patients with chronic glomerulopathies that was non-reversible on cessation of therapy. Nephrotoxicity from combined sirolimus and tacrolimus has been described in patients with T1D undergoing islet transplantation, particularly where there is underlying pre-existing renal damage from diabetes.

The majority of islet transplant recipients receiving sirolimus in conjunction with tacrolimus have experienced transient mouth ulceration and lower extremity edema; perinephric edema and a high incidence of benign ovarian cysts have also been described in islet recipients in association with sirolimus. Pneumonitis and colitis have also occurred. The most common (> 30%) adverse reactions are: oral aphthous ulcers, peripheral edema, hypertriglyceridemia, hypertension, hypercholesterolemia, increased creatinine, abdominal pain, diarrhea, headache, fever, urinary tract infection, anemia, nausea, arthralgia, pain, and thrombocytopenia.

Concerns have been raised by the FDA regarding trials of combined sirolimus/tacrolimus in liver transplant recipients, where there has been a statistically increased risk of hepatic artery thrombosis and late death in sirolimus-treated recipients. A careful analysis of these events does not establish causative association between sirolimus/tacrolimus and thrombosis or death events. There was no increased association with portal venous thrombosis in the liver transplant trials. While sirolimus continues to be used off-label in islet recipients, there is not

presently felt to be an association between portal thrombus formation in islet recipients and the use of sirolimus or tacrolimus.

#### 1.4.1.2 TACROLIMUS (PROGRAF®)

Tacrolimus (Prograf®, FK506) has been in wide clinical use for the prevention of allograft rejection since 1994 when the FDA approved it after several years of testing. Tacrolimus is a macrolide antibiotic which inhibits calcineurin after binding intracellularly to FKBP12 within T cells, inhibiting IL-2 transcription. Tacrolimus is invariably administered with other immunosuppressive agents but is known to be associated with several side effects including hypertension, diabetes, nephrotoxicity, hyperkalemia, dyslipidemia, pruritis, neurotoxicity, neurologic sequelae (including tremor, ataxia, and extremely rarely central pontine myelinolysis), posterior reversible encephalopathy syndrome (PRES), progressive multifocal leukoencephalopathy (PML), interstitial lung disease, BK nephropathy, nausea, vomiting and diarrhea (see product monograph for details). In 205 kidney transplant recipients receiving tacrolimus, the principal AEs were neurologic (tremor [54%], headache [44%], insomnia [32%], paresthesia [23%]) and gastrointestinal (diarrhea [44%], nausea [38%], constipation [35%]) complaints, hypertension (50%), and kidney dysfunction (52%); hyperkalemia (31%) and hyperglycemia (22% in previous non-diabetics) also occurred. The severity of these events appears to be dose dependent, with very high plasma levels also producing delirium, seizures, and coma. Complications can be minimized with the relatively low dose long-term therapy typically used in islet transplant trials.

#### 1.4.1.3 CYCLOSPORINE (NEORAL®)

Cyclosporine is associated with renal dysfunction, tremors, hirsutism, hypertension, and gum hyperplasia.

#### 1.4.1.4 MYCOPHENOLATE MOFETIL (CELLCEPT®) AND MYCOPHENOLATE SODIUM (MYFORTIC®)

CellCept® and Myfortic® are associated with: diarrhea, leucopenia, vomiting, and evidence of higher frequency of certain types of infections, some of which can be fatal. CellCept® and Myfortic® may increase the risk of developing lymphoproliferative disease, lymphomas, and other malignancies, particularly of the skin, and have been known to cause fetal harm (congenital malformations and pregnancy loss) when administered to a pregnant woman. Cases of progressive multifocal leukoencephalopathy, sometimes fatal, and pure red cell aplasia have been reported in patients treated with CellCept® or Myfortic® in combination with other immunosuppressive agents.

Contraception requirements are outlined in the eligibility criteria.

### **1.4.2 Risk of Study Procedures**

The procedures involved with the care of research subjects undergoing clinical islet transplantation include risks pertaining to: a) blood draw testing, b) metabolic stimulation testing, and c) specific follow-up testing.

#### **1.4.2.1 METABOLIC STIMULATION TESTING**

The risks associated with metabolic testing are generally regarded as minor. Placement of IV cannulae may be associated with pain and discomfort at the puncture site, bruising, bleeding, displacement, interstitial infusion of fluids, local vein thrombosis, infection or thrombophlebitis.

The administration of bolus glucose by mouth or intravenously may lead to acute hypoglycemia or hyperglycemia, or rarely may induce ketoacidosis.

#### **1.4.2.2 BLOOD DRAW TESTING**

Peripheral blood draws performed during these research studies will not exceed 450 mL per six-week period. The subject may experience some discomfort at the site of the needle entry, and there is risk of bruising at the site. There is a remote risk of fainting or local infection.

### **1.4.3 Benefits**

The major benefit of this study will be to provide further information on the duration and quality of function of islet grafts beyond the CIT parent study's follow up period.

## **2. OBJECTIVES**

### **2.1 Primary Objective**

The primary objective is to provide extended follow-up for safety and efficacy and to support continued islet graft function to participants previously enrolled in CIT02, CIT03, CIT04, CIT05, CIT06, or CIT07.

### **3. SELECTION OF SUBJECTS**

#### **3.1 Inclusion Criteria**

Patients who meet all of the following criteria are eligible for participation in the study:

1. Participation in any of the following CIT parent studies: CIT02, CIT03, CIT04, CIT05, CIT06, and CIT07.
2. Willingness of participants to continue to use an approved method of contraception during and 4 months after study participation.
3. Ability to provide written informed consent.

#### **3.2 Exclusion Criteria**

Patients who meet any of these criteria are not eligible for participation in the study:

1. For female subjects: Positive pregnancy test, presently breast-feeding, or unwillingness to use effective contraceptive measures for the duration of the study and 4 months after discontinuation. For male subjects: intent to procreate during the duration of the study or within 4 months after discontinuation or unwillingness to use effective measures of contraception. Oral contraceptives, Norplant®, Depo-Provera®, and barrier devices with spermicide are acceptable contraceptive methods; condoms used alone are not acceptable.
2. Received an islet transplant in a non-CIT research study.
3. Any medical condition that, in the opinion of the investigator, will interfere with safe participation in the trial.

## 4. STUDY DESIGN

This is an open-label, multi-center cohort study for participants from the CIT02, CIT03, CIT04, CIT05, CIT06, and CIT07 studies who continue to have islet graft function. These participants will continue immunosuppressive medications under CIT08 and will be assessed for islet function on an annual basis.

### 4.1 Study Endpoints

#### 4.1.1 Primary Endpoint

The primary endpoint is duration of sustained **islet allograft function** as determined by evidence from MMTT of c-peptide production at each anniversary of the final transplant. A c-peptide level greater than or equal to 0.3 ng/mL at 0, 60, or 90 minutes will be considered evidence of islet allograft function.

#### 4.1.2 Secondary Endpoints

Secondary endpoints include the following:

- Serum creatinine and calculated eGFR at each annual study visit
- Incidence of serious adverse events during the 12-month period preceding each annual study visit
- Insulin requirements during a one-week period preceding each annual study visit
- Incidence of severe hypoglycemic events during the 12-month period preceding each annual study visit
- HbA1c levels at each annual study visit
- All causes of mortality
- Presence of alloantibody after graft failure, in the absence of immunosuppression

## **5. STUDY TREATMENT REGIMEN**

### **5.1 Immunosuppression Medications**

The marketed immunosuppressive medications in this protocol will be obtained by prescription unless provided by the study through the drug distributor. Generic brands are allowed, when available.

#### **5.1.1 Drug Accountability**

Under Title 21 of the Code of Federal Regulations (21CFR §312.62), the investigator is required to maintain adequate records of the disposition of immunosuppressants provided for the study through the drug distributor, including the date and quantity of the drug received, to whom the drug was dispensed (subject-by-subject accounting), and a detailed accounting of any drug accidentally or deliberately destroyed.

Records for receipt, storage, use, and disposition will be maintained by the study site. A drug-dispensing log will be kept current for each subject. This log will contain the identification of each subject and the date and quantity of drug dispensed.

All records regarding the disposition of the study-provided immunosuppressants will be available for inspection by the clinical trial monitor.

### **5.2 Concomitant Medications**

Antibacterial, antifungal, and antiviral prophylaxis, insulin therapy, and other standard therapies will be provided per site-specific practices. The cost of these drugs will not be covered under this protocol. Substitution of non-brand name generic equivalents for those protocol required medicines is permitted to reduce cost to the patients and/or their insurance companies.

### **5.3 Rescue Medications**

Rescue therapy will not be initiated in this protocol to treat suspected rejection. Immunologic surveillance methods that would allow diagnosis of islet allograft rejection early enough for timely intervention have yet to be identified and validated.

### **5.4 Prohibited Medications**

None.

## **6. CRITERIA FOR PREMATURE TERMINATION OF THE STUDY**

### **6.1 Subject Withdrawal Criteria**

Subjects may be prematurely terminated from study for the following reasons:

1. The subject elects to withdraw consent from all future study activities, including follow-up.
2. The subject is “lost to follow-up” (*i.e.*, no further follow-up is possible because attempts to reestablish contact with the subject have failed).
3. The subject dies.
4. The investigator determines that it is not in the subject’s best interest to continue.
5. The subject enrolls and begins study treatment in another investigational protocol for islet transplantation while enrolled in this study.

Subjects who prematurely terminate from this study will not be replaced. If possible, assessment of adverse events will be collected prior to termination (see section 8). Data from such subjects obtained before withdrawal of consent or before being lost to follow-up will be used in the intent-to-treat analysis. If a subject with functioning transplanted islets chooses to withdraw from the protocol, s/he will be informed of their risk for losing his/her islet graft and becoming sensitized if s/he chooses to discontinue immunosuppressive therapy and return to his/her original method of insulin management.

### **6.2 Subject Stopping Rules**

#### **6.2.1 Subject Stopping Rules**

None.

#### **6.2.2 Study Stopping Rules**

None.

## 7. STUDY PROCEDURES

### 7.1 Enrollment and Screening

Patients who meet the general inclusion criteria for this study will be approached regarding their participation in this study. The study procedures, risks, and potential benefits will be discussed with the potential study subject in lay language. The potential study subject will have an opportunity to review the informed consent and ask questions.

Once informed consent has been obtained, the subject will be enrolled. Subject eligibility will be confirmed through information collected from their most recent CIT study visit. If more than 90 days have elapsed since the subject's last CIT study visit, then the screening visit assessments should be performed in order to confirm eligibility.

### 7.2 Follow-up Visits

Subjects will be followed in this study after termination from the CIT parent study until the end date of the CIT08 study. Follow-up is comprised of quarterly visits done locally for safety monitoring and annual visits at the study center to assess graft function (if applicable) and safety.

Retrospective medical chart review will be conducted as needed to collect available follow-up information due to:

- delayed enrollment in CIT08 after termination from the CIT parent study
- the time period between termination from CIT08 prior to extension of the duration of follow-up and subsequent re-enrollment

This retrospective chart review will collect evidence of graft failure in addition to the follow-up assessments outlined in Appendix 1.

Subjects are allowed to concurrently enroll in and be screened for a non-CIT islet transplant study at any point during participation. Once study treatment in the non-CIT study is initiated, they will be withdrawn from CIT08 (see section 6.1).

Subjects with confirmed **graft failure** will not complete metabolic assessments. Subjects who experience graft failure and subsequently stop immunosuppression will have alloantibody assessed 3 months after their last dose of immunosuppression.

### 7.3 Visit Windows

If the screening visit occurs within 90 days of the subject's final parent study visit, the results from the final parent study visit should be used. If the screening visit occurs more than 90 days after the final parent study visit, then the screening assessments must be repeated. Annual study visits will occur within plus or minus 30 days of the anniversary of the subjects' last parent study visit. Quarterly local visits will occur within plus or minus 14 days.

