## Protocol Synopsis

Title	Islet Transplantation in Type 1 Diabetes
Clinical Phase	Phase 3
IND Sponsor	DAIT/NIAID/NIH
IND Number	Exempt
Activation Date	June 2011
Accrual Objective	Approximately 75 subjects
Accrual Period	N/A
Follow-up Period	Varies; the CIT08 follow-up period begins after termination from the CIT parent study and ends on the final date of the CIT08 study, 01Jul2017.
Study Design	A single-arm, multi-center cohort study in islet transplantation
Treatment Description	Subjects who have received an islet transplant during participation in CIT02, CIT03, CIT04, CIT05, CIT06, or CIT07 will undergo additional follow-up, including annual assessments of graft function (if applicable) and safety.
Primary Endpoint	The primary endpoint is duration of sustained islet allograft function as determined by evidence from MMIT of C-peptide production at each anniversary of the final transplant. A C-peptide level greater than or equal to 0.3 ng/mL at 0, 60, or 90 minutes will be considered evidence of islet allograft function.
Secondary Endpoints	Secondary endpoints include the following: 

• Serum creatinine and calculated eGFR at each annual study visit

• Incidence of serious adverse events during the 12-month period preceding each annual study visit

• Insulin requirements during a one-week period preceding each annual study visit

• Incidence of severe hypoglycemic events during the 12-month period preceding each annual study visit

• HbA1c levels at each annual study visit

• All causes of mortality

Inclusion Criteria	

1. Participation in any of the following CIT parent studies: CIT02, CIT03, CIT04, CIT05, CIT06, and CIT07.

2. Willingness of participants to continue to use an approved method of contraception during and 4 months after study participation.

3. Ability to provide written informed consent.

Exclusion Criteria	

1. For female subjects: Positive pregnancy test, presently breast-feeding, or unwillingness to use effective contraceptive measures for the duration of the study and 4 months after discontinuation.

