## 10. STATISTICAL CONSIDERATIONS AND ANALYTICAL PLAN

### 10.1 Study Endpoint Assessment

#### 10.1.1 Primary Endpoint

The primary endpoint is time to islet graft failure. The purpose of the analyses will be to estimate the probability of islet graft failure as a function of time from entry into the study. Life table methods will be used to estimate the survival curve and provide confidence intervals for the probability of islet graft survival for selected time points.

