## Appendix 1. Schedule of Events for Extended Follow-up

Visit schedule based on anniversary of last islet transplant in CIT parent study; visit schedule repeats each year.	Timing	SC	Local Visits 			On-Site Visit
			3 month	6 month	9 month	Anniversary of Final Islet Transplant
	Visit #	0	See MOP for Table of Visit Numbers			
Visit Window (specified in days)		- 90	±14	±14	±14	± 30
GENERAL ASSESSMENTS						
Informed Consent		X				
Evaluate Inclusion/Exclusion Criteria		X				
Physical Exam		X 				X
AE /Hypoglycemic Events/Toxicity Assessment 		X 	X	X	X	X
Calculated GFR		X 				X
Insulin use		X 	X	X	X	X 
Urine pregnancy test (females)		X				
LOCAL LABORATORY ASSESSMENTS						
CBC (WBC + Diff & Plat) 		X 	X	X	X	X
Chemistry 		X 	X	X	X	X
Lipids 		X 				X
Alloantibody		Collect 3 months after immunosuppressive medication is stopped following graft failure.				
CENTRAL LABORATORY/METABOLIC ASSESSMENTS						
HbA1c 		X 				X
Fasting serum gluc/c-pep & serum creatinine 		X 				X
MMTT 		X 				X
CARDIOVASCULAR ASSESSMENTS						
Carotid intimal thickness (IMT)		Collect at 5 years post-initial-islet transplant visit in subjects who completed the baseline carotid IMT assessment in their CIT parent study. 				
IMMUNOSUPPRESSION LEVELS						
Blood Trough Levels (if applicable) 		X 	X	X	X	X
Visit schedule based on anniversary of last islet transplant in CIT parent study; visit schedule repeats each year.	Timing	SC	Local Visits 			On-Site Visit
			3 month	6 month	9 month	Anniversary of Final Islet Transplant
	Visit #	0	See MOP for Table of Visit Numbers			
Visit Window (specified in days)		- 90	±14	±14	±14	± 30
MECHANISTIC ASSAYS - University of Pennsylvania Sub-Study Only						
Autoantibody 				X		X
Immunophenotyping 				X		X
Cytokine profiling 				X		X
Glucose-potentiated arginine 						X
ARCHIVED SAMPLES						
Serum						X

---

 These visits are performed locally but can be done on site if preferred.

 Only collect if screening is  $\geq 90$  days since final parent study visit. Otherwise, results from final parent study visit should be used for screening (Visit 0).

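### CIT08 section 7.3 ties the annual visit to the last parent-study visit, but the primary endpoint, synopsis and Appendix 1 tie it to the final transplant, and section 10.1.1 uses a third clock

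*Protocol*

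**What the plan says.** All of this is current text of the CIT08 follow-up protocol.

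- Section 7.3 (Visit Windows): "Annual study visits will occur within plus or minus 30 days of the anniversary of the subjects' last parent study visit".
- Section 4.1.1 defines the primary endpoint as the duration of sustained graft function, "as determined by evidence from MMTT of c-peptide production at each anniversary of the final transplant". The synopsis agrees: "C-peptide production at each anniversary of the final transplant".
- Appendix 1 heads its table "Visit schedule based on anniversary of last islet transplant in CIT parent study; visit schedule repeats each year". It labels the annual on-site column "Anniversary of Final Islet Transplant", with a window of ±30 days.
- Apart from screening, Appendix 1 schedules the MMTT only at that annual visit.
- Section 10.1.1 calls the primary endpoint time to islet graft failure and sets out to "estimate the probability of islet graft failure as a function of time from entry into the study".
- By the synopsis, CIT08 follow-up "begins after termination from the CIT parent study and ends on the final date of the CIT08 study, 01Jul2017".

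**The concern.** The anchor of the annual visit decides when graft function is measured, because the MMTT that shows it is done only then. A site working from section 7.3 and a site working from Appendix 1 would put the same subject's MMTT on different dates. Each would comply with one part of the protocol and could deviate from the other. If 7.3 is followed, the test is not tied to the time points that the endpoint names.

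Section 10.1.1 adds a third clock. The endpoint counts from the final transplant, the visit window from the last parent-study visit, and the survival curve from entry into CIT08. An MMTT not done at the intended time cannot be recovered at analysis, so this is better settled in the protocol than left to the analysis plan.

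**Working it through.** No sample size, power or error rate is involved, and the plan gives no figure to reproduce. The check is date arithmetic on CIT04, the only parent study whose schedule is shown.

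**Inputs**
- CIT04 Appendix 4 counts second-year visits in weeks from the Day 365 visit after the final transplant. The W52 (AY) visit is therefore 364 days after that visit, ±5 days.
- The Day 365 visit has two windows. CIT04 Appendix 1 (Visit 21) and the introduction to Appendix 2 give ±5 days. CIT04 section 4.1.2.1 and Appendix 3 give ±14 days.
- CIT08 section 7.3 allows a further ±30 days.

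**Completers whose last parent-study visit is W52 (AY)**

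Nominal day of the last visit: 365 + 364 = 729, against a two-year anniversary at day 730. The gap is 1 day.

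Distance of a 7.3-compliant MMTT from the transplant anniversary, in 365-day years:

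D = u1 + u2 + u3 − 1

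Here u1 is the Day 365 deviation (±5 or ±14), u2 the W52 deviation (±5) and u3 the annual-visit deviation (±30).

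| Day 365 window | Earliest D | Latest D | Share with \|D\| > 30, uniform windows |
|---|---|---|---|
| ±5 | −5 − 5 − 30 − 1 = −41 | 5 + 5 + 30 − 1 = +39 | 5.7% |
| ±14 | −14 − 5 − 30 − 1 = −50 | 14 + 5 + 30 − 1 = +48 | 12.2% |

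The shares come from simulation with each u uniform over its window. The documents say nothing about how the windows are used in practice.

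The anchors themselves (u1 + u2 − 1) differ by at most 20 days, so the two ±30-day windows always overlap for these subjects. One visit can satisfy both rules.

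**If the Y2 (AY) visit is the last one.** CIT04 Appendix 4 also lists a visit two years after the initial transplant, ±30 days. If that is the last visit of a single-transplant subject, the MMTT can be 30 + 30 = 60 days off. About 25% would lie outside ±30 days under the same uniform assumption.

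**Last visit far from an anniversary.** Exit times are not in the documents, so these are illustrations:
- Last visit at W12 (AY): day 365 + 84 = 449, an anchor offset of 84 days.
- Last visit at W24 (AY): day 365 + 168 = 533, an anchor offset of 168 days.
- The largest possible offset is half a year, about 182 days.

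Once the offset exceeds 30 + 30 = 60 days, the two windows no longer overlap. Every annual MMTT done under 7.3 then misses the Appendix 1 window.

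**The case against.** The best defence is that the two rules barely differ for subjects who complete CIT04. The nominal gap is a day, the windows overlap, and Appendix 1 states the transplant anchor both in its header and in the visit column. A site using it would stay within 30 days of the anniversary. Graft function is tested only yearly, so the failure time is already known only to within about a year, and a shift of weeks adds little. This stands, and it limits the effect for these subjects.

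A reader might infer that 12% of annual tests will miss their window. The documents do not support that. The figure needs the wider Day 365 window, uniform use of every window, and sites that disregard Appendix 1. With the ±5-day window it is about 6%.

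A reader might also infer that six-month offsets are common. CIT04 section 5.7.2 keeps subjects who stop treatment in the study, and Appendix 5 follows them to two years after the last transplant. Most grounds for leaving CIT04 in section 6.1 make entry to CIT08 unlikely, and CIT08 section 1.3 speaks of subjects who have completed their parent study. Yet CIT08 section 3.1 requires only participation, so such entrants remain possible. How many there are is not stated.

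Nor can it be said that subjects from different parent studies are tested at different times since transplant. The schedules of CIT02, CIT03, CIT05, CIT06 and CIT07 are not shown.

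Finally, the anchor in 7.3 lies close to the analysis origin in 10.1.1, because results of the final parent visit serve as Visit 0 when screening falls within 90 days. Amending 7.3 alone would therefore leave a conflict with 10.1.1. That is correct, and the fix has to cover both.

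**Conclusion.** The contradiction is real. Section 7.3 is the one visit-timing passage that departs from the final-transplant anchor, and it governs the only scheduled post-screening measurement of the primary endpoint. Section 10.1.1 then uses a time origin that matches neither the endpoint nor Appendix 1.

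The size is modest where it can be calculated. For CIT04 completers counted through W52 (AY), the gap is about 1 day nominally. If 7.3 alone is followed, the extremes are −41 to +39 or −50 to +48 days, depending on which Day 365 window applies. The 6% to 12% outside ±30 days rests on uniform use of the windows. Offsets of several months are possible under the entry criteria but cannot be quantified from these documents.

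What is affected is when graft failure is detected and which anniversary a test is assigned to. No sample size or error rate changes. The protocol should be corrected, but the point does not undermine the study.

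**What to change.** Reconcile section 7.3 with the synopsis, section 4.1.1 and Appendix 1 by stating the annual visit as ±30 days around the anniversary of the final islet transplant. Keep the last parent-study visit only for the 90-day screening rule. Every annual MMTT done in window is then at most 30 days from the anniversary that the endpoint names.

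In the same amendment, align the time origin in section 10.1.1 with the endpoint and state that the survival analysis uses actual MMTT dates. If time is counted from the final transplant, say how subjects enter the risk set, since CIT08 observation starts later than that.

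The cost is one changed sentence in 7.3 and a short clarification in 10.1.1, with no added visits or tests. The change concerns when an endpoint is measured, not treatment.
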